6.3 Missing data

The primary variables will be assumed to be negative, A “No” answer, if no positive answer is reported.

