Appendix 1: SAS variable names used in the received data set

The table below presents the SAS variable names as they appear in the original SAS data set received.

Variables	SAS variable names
Age group	
Gender	
Weight	
Height	
BMI	
Occupational status	
Education level	
Household income	
Household count	
Children living at home	
Smoking habits	
Chronic disease (Yes/No)	
Parents ethnic origin	
Skin type	
Sun exposure (July to October 2020)	
Dietary intake (Yes/No):	
Vitamin D supplement	
Omega-3 supplement	
Cod liver oil	
Fatty fish intake	
Compliance	
Airways infections	
SARS-CoV-2-tested	
Self-reported free-text side effects	
Laboratory measurements:	
Vitamin D	
Omega-3 index	
Baseline serology	

Primary variables:	
1. Serious COVID-19 (MSIS-confirmed COVID-19 with Dyspnoea, hospitalisation, or death)	CLOC_primary_1_severe_c19
2. COVID-19 defined by positive PCR obtained from MSIS	CLOC_primary_2_msis_status
3. A negative MSIS SARS-CoV-2 test	CLOC_primary_3_negative_tests
4. Self-reported airways infection	CLOC_primary_4_selfrep_airway

Description of the calculation of the four primary variables

- **First primary:** Serious COVID

- *CLOC_primary_1_severe_c19*

- Created by merging *deriv_sym_dyspnea_post_cov_yn_ever* and *deriv_hosp_post_cov_yn_ever* (see description below).
 - 1 = ever answered yes for dysp or hosp
 - 0 = only answered no for dysp or hosp
 - 999 = has filled out forms, has not answered for dysp or hosp question
 - NA = has not filled out forms / not tested positive (second primary)

- Only participants fulfilling the criteria for the second primary, will be included in this analysis. In addition, participants who have tested positive within one week after start of oil consumption are excluded from the analysis (*exclude_Msis_transtart7d*).

- Dyspnoea criteria

- Variable: *deriv_sym_dyspnea_post_cov_yn_ever*

- Answered dyspnoea in forms (R1-R6, E2, Q1) submitted after positive cov test (MSIS)
 - 1 = ever answered yes in any form
 - 0 = only answered no in any form
 - 999 = has filled out form, has not answered dypnoea question
 - NA = has not filled out form

- Hospitalized criteria

- Variable: *deriv_hosp_post_cov_yn_ever*

- Answered hospitalized because of COVID in forms (B1, B2, R1-R6, E2) submitted after positive cov test (MSIS)
 - 1 = ever answered yes in any form
 - 0 = only answered no in any form
 - 999 = has filled out form, has not answered hospitalized question

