cancer	difference in lung cancer incidence in	of vitamin D in cod
	postmenopausal women (RR 0.90, 95% CI 0.39 to	liver oil lung cancer
	2.08; 3 RCTs, 37601 women; low-certainty evidence).	indidence?

Benefit/Risk Assessment

Based on existing literature and data from Koronastudien, we have identified cod liver oil as a supplement that may prevent Covid-19 and or reduce the severity of the disease and found that the benefit of testing this in a randomized study far outweighs the risks. A full benefit/risk assessment is found in the Ethics section.

3. Objectives and endpoints

Based on the encouraging results from Koronastudien as well as existing evidence from the literature, we aim to investigate whether cod liver oil can prevent Covid-19, serious Covid-19, or other respiratory tract infections.

We also aim to explore and confirm already known health effects and possible new health effects, in particular rare adverse events associated with cod liver oil use. This will be done during a follow-up period of up to two years after the end of the cod liver oil period

We hypothesize that:

Intake of cod liver oil can prevent Covid-19 disease Intake of cod liver oil can prevent serious Covid-19 Intake of cod liver oil can prevent other airway infections

These hypotheses will be tested in a triple-blinded randomized placebo-controlled study where 80.000 participants will be assigned to cod liver oil or placebo in a 1:1 ratio.

The safety of cod liver oil will be explored.

Finally, it is a separate aim of the study to identify the mechanisms of action of any health effects seen.

Definition of endpoints

A. Number of participants diagnosed with serious Covid-19 (primary endpoint)

The number of participants with first time SARS-CoV-2 positive nasopharyngeal and or pharyngeal swabs (or any other sample used for detection of current disease) analyzed by reverse transcriptase quantitative polymerase chain reaction (RT-qPCR) nucleic acid amplification test or antigen tests [18] used by accredited Norwegian microbiology laboratories in the period from one week after the start of cod liver oil/placebo taking to the end of the study period together with any of the following:

A) Self-reported dyspnea concurrent with the positive test

OR

B) self-reported hospitalization caused by Covid-19 concurrent with the positive test OR

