In rare instances, it may be necessary for a participant to permanently discontinue study intervention. If study intervention is permanently discontinued, the participant will remain in the study to be evaluated for relevant endpoints unless the participants want to also withdraw.

Participant Discontinuation/Withdrawal from the Study

A participant may withdraw from the study at any time at his/her own request or may be withdrawn at any time at the discretion of the investigator for safety, behavioral, or compliance reasons.

The participant will be permanently discontinued both from the study intervention and from the study at that time.

The participant may also withdraw the consent to use some of his or her data as described in the consent form.

Lost to Follow Up

A participant will be considered lost to follow-up if he or she repeatedly fails to return for scheduled visits and is unable to be contacted by the study and data on registries are no longer recorded (this will mostly be participants moving abroad).

Cod Liver Oil for Covid-19 Prevention Study, protocol version 1.2, November 10, 2021

8. Study Assessments and Procedures

Endpoint Ascertainment and Validation

Se also definition of endpoints in chapter 3.

Endpoint ascertainment will be done by obtaining endpoint data from relevant registries. The connection between the CLOC study and the registries will be made by the Norwegian Personal Identity Number (PIN), which ensures unambiguous identification of every subject. The PIN number is validated by 2-factor authentication when the informed consent is signed electronically.

Registry data will be compared to the self-reported symptoms. In cases where an episode of respiratory illness evidenced by a positive PCR or culture is not accompanied by a symptom report form, the patient will be encouraged to complete a symptom form.

Diagnoses in hospitalized patients and outpatient visits are reported to the Norwegian Patient Registry (NPR), while deaths are reported to the Causes of Death Registry.

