Covid-19- related diagnoses and deaths in these registries are essential endpoints in the study and will be validated through inspection of the relevant hospital records (NPR) or hospital- or GP records (CDR). This will be done by contacting the hospital or GP for a copy of the relevant information from their records, which will be recorded in the CRF together with a conclusion about Covid-19 being the cause of the hospitalization or death. The information will also be presented for another independent and blinded physician for a second opinion, and in cases of discrepancy; the information will further be inspected by a blinded endpoint-verification committee for a final decision. It will be arranged for the endpoint-verification committee to have access to interview the treating physician.

The endpoint of subjective dyspnea during Covid-19 will be based on self-reporting (yes/no), but Covid-19 diagnosis is verified by the Norwegian Surveillance System for Communicable Diseases (MSIS).

Safety Assessment

Cod liver oil is recommended as a part of the Norwegian diet in official dietary recommendations and no safety assessment will be conducted during the cod liver oil/placebo taking period. See Ethics section.

Blood collection

Blood will be collected for the purpose of monitoring compliance and for the study itself. Blood will be collected according to the standard procedure described in Oslo University Hospitals' quality control system, and either venipuncture or dried blood spots will be used.

- Random blood collection for Compliance (either venipuncture or dried blood spot)
- Baseline and follow up for biobanking (either venipuncture or dried blood spot)
- Surplus material already stored in existing biobanks including treatment-biobanks will also be collected from the participants, and either stored in the study biobank or analyzed immediately (or both)

Blood samples will be analyzed for vitamin D levels (25(OH)D), EPA and DHA levels, and other biochemical parameters. The material will be stored in the study biobank for analyses to explore and explain the main results of the study. These analyses can include both biochemical, immunological, and molecular biology analyses and will be determined based on the results of the investigation.

Biobank

A study-specific biobank for the duration of the study until five years after all participants are dead will be created.

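### The protocol contradicts itself on the source of the hospitalisation component of the first primary; the SAP takes it only from forms sent after the positive test, so an admitted survivor with no later form counts as not serious.

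*SAP*

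**What the plan says.** The protocol gives two accounts of where hospitalisation comes from.

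- Self-report. Protocol section 3, endpoint A, lists "self-reported hospitalization caused by Covid-19 concurrent with the positive test" as one of three qualifying conditions. Section 9 (Sample Size Determination) repeats that both dyspnoea and hospitalisation are self-reported.
- Registry. Protocol section 8 (Endpoint Ascertainment and Validation) states: "Endpoint ascertainment will be done by obtaining endpoint data from relevant registries". It places hospital diagnoses in the NPR and says of COVID-19 that "diagnoses and deaths in these registries are essential endpoints in the study". These are to be checked against hospital records, with a blinded second physician and a committee for disagreements. The only component of serious COVID-19 that section 8 describes as self-reported is dyspnoea.

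SAP 3.3 and 6.1 say hospitalisation without naming a source. SAP Appendix 1 settles it in favour of forms: "Answered hospitalized because of COVID in forms (B1, B2, R1-R6, E2) submitted after positive cov test (MSIS"). Dyspnoea is handled in the same way: "Answered dyspnoea in forms (R1-R6, E2, Q1) submitted after positive cov test (MSIS"). The composite is "Created by merging *deriv_sym_dyspnea_post_cov_yn_ever* and *deriv_hosp_post_cov_yn_ever* (see description below"). A positive participant with no such form is coded under "NA = has not filled out forms / not tested positive (second primary").

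The missing-data rule is in SAP 6.3: "The primary variables will be assumed to be negative, A “No” answer, if no positive answer is reported". SAP 4.2 and 6.1 say the same.

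**The concern.** Consider a participant who tests positive in MSIS, is admitted with COVID-19, survives, and returns none of the listed forms afterwards. Both component variables are NA, and the missing-data rule turns NA into No. The participant is analysed as free of serious COVID-19, although the protocol plans to hold an NPR record of the admission. The same happens if a later form is returned but the hospitalisation item is left blank and dyspnoea is not reported.

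This is the first endpoint in the fallback sequence. It carries α = 0.018 and was planned at only 70% power on few events, so lost events are costly. If non-return differed between arms, the difference would also shift the risk ratio. A source that does not depend on the participant sending a form is already listed in the protocol.

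**Working it through.** **1. Trace the rule through Appendix 1.** All cases are MSIS-positive and outside the first-week exclusion.

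| Course after the positive test | Hospitalisation variable | Analysed as |
|---|---|---|
| Admitted, says yes in any later listed form | 1 | Serious |
| Admitted, reports dyspnoea but not the admission in a later listed form | 0 or 999 | Serious (through dyspnoea) |
| Admitted, later form has the item blank and no dyspnoea reported | 999 | Not serious |
| Admitted, survives, no later listed form | NA | Not serious |

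Death has its own criterion, based on the National Population Register plus hospital records or relatives. No comparable outside source exists for hospitalisation.

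**2. Reproduce the planned sample size.** Inputs from SAP 3.3: α = 0.018 (two-sided reproduces the figure), control incidence p₁ = 0.0025, 40% reduction so p₂ = 0.0015, power 70%, 1:1 allocation. With p̄ = 0.002:

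n per arm = [z₀.₉₉₁·√(2p̄(1−p̄)) + z₀.₇₀·√(p₁(1−p₁)+p₂(1−p₂))]² / (p₁−p₂)²
= [2.3656 × 0.063182 + 0.5244 × 0.063178]² / 0.001² ≈ 33,342

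The total is 66,684, against the stated 67,000. The planned figure reproduces. It assumes that every serious case is captured: 33,500 × 0.0025 ≈ 84 control events and 33,500 × 0.0015 ≈ 50 on cod liver oil.

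**3. Equal loss in both arms.** Let h be the share of serious cases that were hospitalised, and m the share of these with no later form. The documents give neither, so both are assumptions. With h = 10–30% and m = 10–50%, the share of events lost is h·m = 1–15%. The risk ratio stays at 0.6, but both incidences are multiplied by (1 − loss):

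Power = Φ{[(p₁−p₂)√n − 2.3656·√(2p̄(1−p̄))] / √(p₁(1−p₁)+p₂(1−p₂))}

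| Events lost | Events at 67,000 (control / cod liver oil) | Power at 67,000 | Power at 80,000 |
|---|---|---|---|
| 0% | 84 / 50 | 70.2% | 78.8% |
| 5% | 80 / 48 | 67.6% | 76.4% |
| 10% | 75 / 45 | 64.9% | 73.8% |
| 15% | 71 / 43 | 62.0% | 71.0% |

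**4. Unequal loss.** With no true effect, the observed risk ratio is (1 − h·m_A)/(1 − h·m_P), where A is cod liver oil and P is placebo. As an illustration, take m_A = 30% and m_P = 10%:

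- h = 10%: 0.97/0.99 = 0.980
- h = 20%: 0.94/0.98 = 0.959
- h = 30%: 0.91/0.97 = 0.938

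At 67,000 this is a difference of about 2 to 5 events, on roughly 80 per arm. By the normal approximation for the log risk ratio, the two-sided type I error moves from 1.8% to between 1.9% and 2.8%. The arm difference in non-return is thus diluted by h.

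**The case against.** The strongest reply is that the SAP follows the protocol's endpoint definition. Sections 3 and 9 both specify self-report, section 8 itself points back to chapter 3 for definitions, and its registry language could be meant for the secondary endpoints of COVID-19 hospitalisation and ICU care. This stands in part: a reader might infer that the SAP departs from the protocol, and the documents do not support that. The conflict is inside the protocol, and the SAP takes one side. It still has to be resolved. If a registry rule governs the secondary hospitalisation endpoint, one participant could be hospitalised there and not serious in the primary.

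Second, there are safeguards. Forms are monthly, there is an end-of-study form, a symptom form is always open, and section 8 says participants with a positive PCR but no symptom form will be encouraged to complete one. A single later yes is enough. This also stands: a gap during the illness loses nothing, and only permanent non-return or an unanswered item does.

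Third, a reader might infer that missing forms fall mainly on true events, so that the endpoint loses its most severe non-fatal cases. That is plausible, but the documents report nothing on form return by severity, and prompting after a positive test could work the other way.

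Fourth, the trial is blinded, so a large arm difference in non-return is unlikely. That weakens the bias argument but not the loss of power.

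Finally, the NPR may not be ready. The documents list it as a planned source and schedule registry data for November 2020 to April 2021, but do not show that an extract is in hand.

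**Conclusion.** The concern holds as an internal contradiction plus a derivation rule that can misclassify true events. Followed as written, Appendix 1 with SAP 4.2, 6.1 and 6.3 scores an admitted survivor with no later listed form as not serious, while protocol section 8 describes a validated source that would identify the case.

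Its size cannot be derived from the documents. Under an assumed equal loss of 5–15% of events, power falls by about 3 to 8 percentage points: 70% to 68–62% at 67,000, and 79% to 76–71% at 80,000. At the targeted enrolment, even the upper end of that range stays just above the planned 70%. The effect is therefore probably modest. The documents do not show a biased risk ratio: bias needs differential non-return, and even 30% versus 10% among hospitalised cases gives 0.98 to 0.94 under no true effect. The change is worth making because the alternative source is already in the protocol and the endpoint has few events to spare.

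**What to change.** Before unblinding, which both documents allow:

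1. Reconcile protocol sections 3, 8 and 9 with SAP Appendix 1, so that one source rule governs the hospitalisation component.
2. Define the component as Yes if either a listed form reports it or the NPR shows an admission for COVID-19, whether or not a form was returned after the test. Prespecify the window in days around the positive test and the diagnosis codes; section 3 says only that the event is concurrent.
3. Keep the self-report-only version as a sensitivity analysis. If the NPR extract will not be available in time, keep self-report as primary and prespecify the NPR-based version as the sensitivity analysis.
4. Report, by arm, the number of MSIS-positive participants with no listed form after the test and the number with the item unanswered.

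The cost is wording in both documents, a linkage to a registry the protocol already lists, and a wait for the extract. The record validation in section 8 adds real work: requests to hospitals, a second blinded reader, and a committee for discrepancies. The NPR does not recover participants whose only qualifying symptom was dyspnoea and who sent no later form; item 4 is what shows how many could be affected.

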6.1 Outcome definitions

Primary variables:

- First primary: Serious COVID-19 (MSIS-confirmed COVID-19 with dyspnoea, hospitalisation, or death)
- Second primary: COVID-19 defined by positive PCR obtained from MSIS
- Third primary: A negative SARS-CoV-2 test (MSIS).
- Fourth primary: Self-reported airways infection

The first incidence of report of any of the above primary variables will be used in the analyses. The specified order will be used for the fallback analyses. The values of all variables will be Yes/No to the condition together with time from one week after start of oil consumption to first reporting of the condition, i.e. Yes (except for third primary variable, where total number of negative tests is reported). Those not reporting a Yes answer, the last reported time will be used as censoring time. The date from one week after oil-consumption starts to the date of reporting of a Yes will be converted to number of days from the first to the second date.

The primary analysis set is the defined ITT sample with missing data on outcome counting as the negative outcome.

Compliance

For sensitivity analyses on compliance, we will define compliant participants as those having taken CLO for at least 2 months. We will also analyse participants based on volume CLO taken (more than 250 ml).

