 - NA = has not filled out form

- Death criteria

- Participant registered as dead/deceased in the National Population Register after a positive cov test (MSIS), but only if the death was related to COVID-19 based on hospital records or information from relatives.

- **Second primary:** New MSIS positive

- *CLOC_primary_2_msis_status*
 - Created from *MSIS_CLOC_test_status*
 - 1 = tested positive for the first time during **CLOC participation period**
 - 2 = only tested negative during **CLOC participation period** (never positive)
 - 3 = untested during **CLOC participation period** (never positive)
- Participants who have tested positive within one week after start of oil consumption are excluded from the analysis (*exclude_Msis_transtart7d*).
- MSIS criteria
 - Variable: *MSIS_CLOC_test_status*
 - 1 = tested positive for the first time during CLOC
 - 2 = only tested neg during CLOC (never positive)
 - *Variables obtained through MSIS (translated): “Test date” and “Test result”*
 - Variable to be analyzed as second primary endpoint identifying only tests registered during the **CLOC participation period** (defined as period from start of cod liver oil/placebo consumption (*deriv_Date_CLO_start_corr*) to June 2, 2021).
- **Third primary: Negative test**
 - *CLOC_primary_3_negative_tests*
 - Generated from *MSIS_CLOC_TotalTests_7d_neg*
 - Sum of total negative tests registered during the period from one week after start of cod liver oil/placebo consumption (*deriv_Date_CLO_start_corr*) to June 2, 2021.
 - 0 if no tests registered
 - Negative test criteria
 - Variable: *MSIS_CLOC_TotalTests_7d_neg*
 - Sum of total negative tests registered during the period from one week after start of cod liver oil/placebo consumption (*deriv_Date_CLO_start_corr*) to June 2, 2021.
 - Supplementary variables
 - *MSIS_CLOC_FirstNegative*
 - Date of first negative test registered during the **CLOC participation period**.
 - *MSIS_CLOC_LastNegative*
 - Date of last negative test registered during the **CLOC participation period**.
- **Forth primary: Self-reported airway infections**
 - *CLOC_primary_4_selfrep_airway*
 - Generated from *deriv_respinf_date_yn*
 - 1 = ever answered yes and provided valid date in any form
 - 0 = only answered no, or provided non-valid date in any form
 - 999 = has filled out form, has not answered airway infections question
 - NA = has not filled out form

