C) death where the Covid-19 infection was wholly or partly responsible as judged by the death certificate, information from relatives or hospital records (see endpoint in the protocol)

B. Number of participants diagnosed with New Covid-19 (primary endpoint):

The number of participants diagnosed with first time SARS-CoV-2 positive nasopharyngeal and or pharyngeal swabs (or any other sample used for detection of current disease) analyzed by reverse transcriptase quantitative polymerase chain reaction (RT-qPCR) nucleic acid amplification test or antigen tests used by accredited Norwegian microbiology laboratories from one week after the start of cod liver oil/placebo taking.

C. A negative SARS-CoV-2 test (primary endpoint)

Covid tests (SARS-CoV-2), real time (RT)-PCR, are mostly obtained because of a suspicion of COVID-19. The number of negative covid tests from one week after starting taking cod liver oil/placebo and to the end of the intervention period. This endpoint has been added as an alternative to the Positive PCR or bacterial culture endpoint (below, secondary endpoint, which is not available at this time).

D. Number of participants with self-reported airway infection (primary endpoint)

The number of self-reported airway infections in the period from one week after starting taking cod liver oil/placebo to the end of the intervention period.

Secondary endpoints

The testing of secondary endpoints will be described in the Statistical Analysis Plan.

- A) Hospitalization for Covid-19
- B) ICU care for Covid-19
- C) Any admissions to hospital
- D) Infection with each of the mentioned pathogens
- E) Visits at GP for infections
- F) Visits at GP
- G) Laboratory confirmed respiratory tract infection (previous primary endpoint)

G) Number of participants with laboratory confirmed respiratory tract infection (this is a previous primary endpoint, which will be studied later when data from laboratories are available):

An airway sample positive for a respiratory pathogen* (either PCR or culture) in the period from one week after the start of cod liver oil/placebo taking to the end of this period

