All blood- and other biological samples collected as part of the study will be stored in this biobank.

Questionnaires and consent forms

Participants will already have completed the Koronastudien questionnaires containing questions about risk factors for Covid-19, supplement use, travel history, cancer, cardiovascular disease, and other previous diseases, skin-type, sunlight exposure, and demographic variables). During the study period, it is expected that 1-2 Koronastudien specific follow-up questionnaires will be distributed, and these will be coordinated to reduce the burden of participation. In addition, the following data will be collected from the sub-study participants using electronic forms:

- Screening questionnaire before inclusion (inclusion and exclusion criteria)
- Consent form. The identity of each participant in Koronastudien is known through the consenting procedure using two-factor authentication with Bank ID. The consent form for Transtudien will be sent as a unique link to existing participants, and consenting will be a simple yes or no checkbox at the end of the form without requiring further identification with Bank ID.
- Baseline questionnaire: Diet including an estimate of vitamin D and n-3 LCPUFA intake and other baseline data collection will be coordinated with a follow-up questionnaire in Koronastudien to reduce participant burden.
- Every month: Compliance, use of supplements, side effects, efficacy of blinding, endpoints
- End of study: FFQ (a validated web-based food frequency questionnaire), risk factors for Covid-19 and other relevant diseases, use of supplements, previous conditions, side effects, efficacy of blinding, endpoints
- Follow-up up to two years: Diet, use of supplements, endpoints.

Participants will also be encouraged to report any symptoms of respiratory tract infections and any possible side-effect during the cod liver oil taking period using an electronic questionnaire available to them at all times during the study period.

Dietary questions on vitamin D and n-3 LCPUFA will be based on the FFQ.

Registries

Data for validation of endpoints, previous diseases, and risk factors will be obtained from the following registries (registry, data to be obtained):

- Causes of death: death, and cause of death
- Hospital records: verification of endpoints
- KUHR: visits to GP and cause of visit
- Norwegian Prescription database:, medications

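### SAP Appendix 1 omits the death certificate that protocol endpoint A(C) accepts, so a COVID-19 death attributable only by certificate is a case under the protocol but not under the SAP

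*SAP*

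**What the plan says.** SAP 6.1 makes death one of three components of the first primary endpoint and names no source for it: "First primary: Serious COVID-19 (MSIS-confirmed COVID-19 with dyspnoea, hospitalisation, or death". SAP 3.3 is equally silent. The source appears only in Appendix 1. There, the fact of death comes from the National Population Register, after a positive MSIS test, and the death counts "only if the death was related to COVID-19 based on hospital records or information from relatives".

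The protocol is wider. Section 3, endpoint A item C, counts "death where the Covid-19 infection was wholly or partly responsible as judged by the death certificate, information from relatives or hospital records". Section 8 (Endpoint Ascertainment and Validation) adds "while deaths are reported to the Causes of Death Registry", and says that COVID-19 events found in the registries "will be validated through inspection of the relevant hospital records (NPR) or hospital- or GP records (CDR"). A second, blinded physician then reviews each case, with a blinded committee where the two differ. The registry list in section 8 includes "Causes of death: death, and cause of death".

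Two further SAP rules decide what happens to a death that is not picked up. Appendix 1 derives `CLOC_primary_1_severe_c19` by merging one dyspnoea variable and one hospitalisation variable, and one of its codes is "NA = has not filled out forms / not tested positive (second primary". SAP 6.3 turns any absent positive answer into a No.

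**The concern.** Serious COVID-19 is tested first in the fallback sequence, at 0.018, and what it passes on depends on its result. Its definition should be the same in both documents. For one component it is not: the same death can be a case under the protocol and a non-case under the SAP.

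The other components cannot be relied on to recover such a death. They come from questionnaires submitted after the positive test, and someone who dies may never submit one.

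Nothing suggests that the change was deliberate. Protocol Amendment 4 (10 November 2021) revised the serious COVID-19 definition by dropping fever and changing the time window, and the current protocol still names the certificate. SAP 1.3 cites the protocol of that date. SAP Amendment 1 (10 December 2021) changed primary endpoints 1 to 4 to agree with the protocol. Neither log mentions a different source for deaths. The protocol says that laboratory data for another endpoint were not available, but says nothing of the kind about causes of death.

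**Working it through.** **1. The two rules side by side**

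| Element | Protocol (sections 3 and 8) | SAP Appendix 1 |
|---|---|---|
| Where deaths are found | Causes of Death Registry | National Population Register |
| Accepted evidence of cause | Death certificate, relatives, or hospital records | Hospital records or relatives |
| Causal test | Full or partial responsibility | A relation to COVID-19 |
| Validation | Hospital or GP records, second blinded physician, blinded committee | None stated |

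The Appendix 1 condition is exclusive, so the certificate cannot be read back in as an unstated example. The protocol lists the certificate and hospital records separately, so one does not stand for the other.

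**2. Which deaths change status**

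Take an MSIS-positive participant who dies, with the positive test inside the counting window.

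| What links the death to COVID-19 | Protocol A(C) | Appendix 1 death criterion |
|---|---|---|
| Hospital record | Case | Case |
| Relatives' information | Case | Case |
| Death certificate only | Case | Not a case |
| GP record only, not certified | Not listed in A(C) | Not a case |

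Whatever the row, an earlier yes to dyspnoea or hospitalisation on a form after the positive test already gives code 1 in Appendix 1. The conflict is therefore confined to the third row without such a yes. That person is coded 0, 999 or NA, and SAP 6.3 makes 999 and NA a No.

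**3. The plan's own figure**

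Inputs from SAP 3.3: incidence 0.25%, reduction 40% (so 0.15% on cod liver oil), alpha 0.018, power 70%, 1:1 allocation. Sidedness is not stated; two-sided is assumed.

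n per arm = [z(1−α/2)·√(2p̄q̄) + z(power)·√(p1q1 + p2q2)]² / (p1 − p2)²

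with p1 = 0.0025, p2 = 0.0015, p̄ = 0.0020. This gives 33,342 per arm, or 66,684 in total, against the stated 67,000. The figure reproduces. (One-sided gives 54,860, which does not match.) Power at 33,500 per arm is 70.2%.

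Expected events at 67,000: 33,500 × 0.0025 = 83.75 on placebo and 33,500 × 0.0015 = 50.25 on cod liver oil, 134 in total.

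**4. How much a loss could matter**

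The documents give no number of deaths. As an assumed range, let deaths be 2% to 10% of serious events and let 20% to 50% of them be attributable only by certificate. The share lost is then 0.02 × 0.20 = 0.4% up to 0.10 × 0.50 = 5%, or 134 × 0.004 = 0.5 up to 134 × 0.05 = 6.7 events. Applying a loss f equally in both arms:

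| f (assumed) | Events lost (134 × f) | Power at 67,000 | N for 70% power |
|---|---|---|---|
| 0 | 0 | 70.2% | 66,684 |
| 0.5% | 0.7 | 70.0% | 67,020 |
| 1% | 1.3 | 69.7% | 67,358 |
| 2% | 2.7 | 69.2% | 68,048 |
| 5% | 6.7 | 67.6% | 70,200 |

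The expected risk ratio does not move: 0.15(1 − f) / 0.25(1 − f) = 0.60 for every f.

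**The case against.** Three stronger readings are tempting, and the documents support none of them.

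- **All certified deaths outside hospital are scored No.** They are not. Relatives' information counts wherever the person died. Dying at home does not rule out a linking hospital record from an earlier contact. An earlier yes to dyspnoea or hospitalisation counts as well.
- **The SAP rule is narrower in every respect.** The list of sources is shorter, but a death that is related to COVID-19 may be as wide a category as one for which it was fully or partly responsible, or wider. The net direction across all deaths is therefore not certain.
- **The endpoint loses material power.** The assumed shares have no basis in the documents. The 5% end would mean about 13 deaths (134 × 0.10 = 13.4) and does not remove those already counted through an earlier yes. People over 75 are excluded, which points to the low end. Even so, power falls by only 2.6 percentage points.

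The protocol also leans on records itself. Section 8 validates registry deaths in hospital or GP records, so in practice a bare certificate might not have settled a case, and endpoint A(C) does not list GP records. That narrows the gap but does not close it: a certified death confirmed only in GP records still fails Appendix 1.

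Finally, rewording the criterion alone would change no coded value, because the derivation has no death term. That objection is right and is met in the fix. Adding the term would not in turn cure the shorter list of sources.

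**Conclusion.** The conflict is real and limited. Appendix 1 and protocol endpoint A(C) define the death component of the first primary endpoint differently, and no amendment entry explains it. The participants affected are MSIS-positive, their death is certified as due wholly or partly to COVID-19, no hospital record or relative links the death to it, and they gave no earlier yes for dyspnoea or hospitalisation.

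How many there are cannot be read from the documents. The number is probably very small, and in a blinded trial the loss should be similar in both arms, which leaves the risk ratio essentially unchanged. Under the assumptions shown, at most about 7 of 134 expected events are lost. The reason to act is that the first-tested endpoint should be the one the protocol defines; the sample size and power statements do not need to change on this account.

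**What to change.** Before unblinding, amend Appendix 1 in two places:

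1. **Death criterion.** Add the death certificate, through the Causes of Death Registry, to the accepted sources. Use the same causal wording as protocol endpoint A(C), and refer to the validation steps in protocol section 8. State there what role GP records play, since endpoint A(C) and section 8 differ on this.
2. **Derivation.** Create a death variable under that criterion and merge it into `CLOC_primary_1_severe_c19`, so that a qualifying death gives code 1 whether or not any form was submitted.

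If the sponsor meant to drop the certificate, the amendment log should say so and give the reason, and the protocol should be brought into line.

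The cost is minor. The text change is short and the registry is already on the protocol's list. The variable list in Appendix 1 shows no cause-of-death item, so those data would have to be linked, and the probably few deaths would need the blinded review that the protocol already promises.
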